2.1.3 Recruitment Strategies

This study will be posted on NIH websites and on NIH social media forums. Participants may also be recruited through self-referrals, physician referrals, and referrals from the NIH Clinical Center (CC) Office of Patient Recruitment.

Patients may also be referred to this study based on confirmation of histology (done by the Laboratory of Pathology) under protocol 06C0014.

2.2 SCREENING EVALUATION

Note: Screening evaluation testing/procedures are conducted under the separate screening protocol 06C0014 OR the consent for study 01C0129 (provided the procedure is permitted on that study) per PI discretion. Assessments and procedures to confirm study eligibility should be completed as follows:

Within 4 Weeks Prior to Protocol Enrollment:

- a. Medical history and physical exam including vital signs and performance status.
- b. Confirmation of histology (archival or fresh tissue if archival tissue is insufficient), PD-L1 expression and mutation status (EGFR and ALK) by the Laboratory of Pathology (any time prior to enrollment). This confirmation will be done under protocol 06C0014 (patients will be co-enrolled).
- c. Blood tests:
 - i. CBC with differential
 - ii. Acute Care Panel: Sodium, potassium, chloride, bicarbonate, creatinine, glucose, BUN, eGFR
 - iii. Hepatic Panel: Alkaline phosphatase, ALT, AST, total and direct bilirubin
 - iv. PT/PTT
- d. Viral Markers (anti-HIV, anti-HCV, HBsAg, anti-HAV IgM); HCV RNA if needed.
- e. 12-lead EKG. Patients with EKG evidence of cardiac ischemia (ST depression/elevation greater than or equal to 2 mm), or arrhythmia will undergo cardiology evaluation to determine eligibility.
- f. Echocardiogram
- g. X-rays, contrast enhanced CT scans of chest, abdomen, pelvis, as well as brain MR, and fused PET-CT scans to evaluate the status of disease (all imaging must be obtained within 4 weeks prior to starting therapy).
- h. Pulmonary function tests (PFTs) with and/or without bronchodilators.
- i. Arterial Blood Gas test (ABG) on room air (to be drawn if pulse oximetry < 90% on room air).
- j. Lupus Anticoagulant and ANA

Within 3 Days Prior to Protocol Enrollment:

a. Women of child-bearing potential will have a urine or serum β hCG pregnancy test.

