1.2.6 Clinical Pharmacokinetics: THU Alone

As previously discussed, THU is a competitive inhibitor of CDA, the enzyme that is largely responsible for the metabolism of cytidine analogues ($\underline{62}$). THU has no therapeutic utility as a separate entity, instead, it is frequently used in clinical studies to inhibit CDA and block the metabolism of cytidine analogues which are co-administered as the active therapeutic agent. The clinical pharmacokinetics of THU have been extensively characterized ($\underline{63}$).

In these studies, with the exception of time-to-peak THU levels, the pharmacokinetics of intravenous, SQ and oral THU at a dose of 200 mg/m² were essentially identical (63). By each route of administration, the initial and secondary half-lives were \sim 8 and 80 minutes, respectively with a plasma half-life or approximately 7 hours. THU elimination was primarily in the urine and with intact drug but no metabolites identified in urine or plasma.

These observations were extended through the use of $[^{14}C]$ -THU (64). In this study, 50 mg/kg $[^{14}C]$ -THU was rapidly cleared from the blood with a plasma half-life of about 1 hour following intravenous administration. Approximately 10% of the same dose was absorbed from the GI tract following oral administration. The main pathway of excretion was through the kidneys with approximately 50% of the administered drug excreted within 24h and 100% elimination within 48h.THU at 10, 25, and 50 mg/kg given 15 minutes before [3H]-cytosine arabinoside (ara-C) at a dose of 0.003 mg/kg produced an approximately two-fold increase in ara-C blood levels at all times measured from 5 minutes to 4 hours, with only slight increases in the half-life of ara-C (64). A dose-related effect of THU upon the deamination of ara-C was obvious only during the time from 15 minutes to 1 hour after the injection of 3H-ara-C. The inhibitory effect of THU upon CDA was also reflected in a considerably increased ratio of ara-C/uracil arabinoside in the urine.

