- 2.1.1.11 Patients must be without evidence of unstable or decompensated myocardial disease; and must have adequate pulmonary reserve evidenced by FEV1 and DLCO \geq 35% predicted; oxygen saturation equal to or greater than 90% on room air by pulse oximetry or ABG (to be drawn if pulse oximetry < 90% on room air).
- 2.1.1.12 No immunosuppressive medications except non-systemic corticosteroids.

2.1.1.13 Patients must have normal organ and marrow function as defined below:

– leukocytes	\geq 3,000/mcL
– absolute neutrophil count	\geq 1,500/mcL (without transfusion or cytokine
	support)
 absolute lymphocyte count 	> 800/mcL
– absolute lymphocyte count – platelets	$\geq 100,000/mcL$
– PT	no more than 2 seconds above the ULN
– total bilirubin	< 1.5 X institutional upper limit of normal
	OR
 direct bilirubin 	\leq ULN for patients with total bilirubin > 1.5
	ULN
– serum albumin	\geq 2.0 mg/dL
– AST(SGOT)/ALT(SGPT)	\leq 2.5 X institutional ULN
- creatinine	\leq 1.6 mg/ml
	OR
- creatinine clearance (eGFR)	$\geq 60 \text{ mL/min}/1.73 \text{ m}^2$ for patients with
	creatinine levels above institutional normal
	at the time DAC-THU and pembrolizumab
	treatment commences.
	d'admont commences.

- 2.1.1.14 Patients with history of brain metastases except those with meningeal carcinomatosis or leptomeningeal disease may be eligible for treatment a minimum of 1 week following completion of gamma knife or whole brain radiotherapy, or 4 weeks following surgical resection of brain metastasis provided post-treatment MR scan reveals no evidence of active disease, and no ongoing need for systemic steroids.
- 2.1.1.15 Patients with laboratory evidence of autoimmune disease (e.g., positive ANA or lupus anticoagulant) without associated symptoms; vitiligo, or mild autoimmunity not impacting the function of organs, such as Hashimoto or psoriasis may be eligible for study.

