3.4 ON STUDY PROTOCOL EVALUATION (APPENDIX 3: STUDY CALENDAR)

3.4.1 Baseline Assessments

Note: Baseline assessments do not need to be repeated if performed during screening in the designated time frame.

Any Time Prior to Initiation of Treatment:

- a. HLA class I and class II analysis of PBMC.
- b. Tumor biopsy if fresh sample from previous biopsy is not available. Note: Samples collected on 06C0014 or any other NCI protocol in which the patient is co-enrolled can be used.

Within 10 Days Prior to Commencing DAC-THU/Pembrolizumab Therapy:

- a. Physical examination including assessment of vital signs and ECOG status.
- b. Chemistries
 - i. Acute Care Panel Sodium (Na), Potassium (K), Chloride (Cl), Total CO2 (bicarbonate), Creatinine, Glucose, Urea nitrogen (BUN),
 - ii. Mineral Panel Albumin, Calcium total, Magnesium total (Mg), Phosphorus
 - iii. Hepatic Panel Alkaline Phosphatase, ALT/GPT, AST/GOT, Total Bilirubin, Direct Bilirubin
 - iv. LD, Total Protein, Total CK, Uric Acid
- c. Fetal hemoglobin
- d. CBC, differential, platelet count, PT, PTT
- e. T, B, NK cell subsets
- f. Urinalysis and culture if indicated
- g. Pulmonary Function Test
- h. Arterial Blood Gas on room air (to be drawn if pulse oximetry <90% on room air).
- i. Research Labs (refer to Appendix 4 for details).

Within 48 Hours Prior to Initiation of DAC-THU/Pembrolizumab Therapy:

a. Women of child-bearing potential will have a urine or serum βhCG pregnancy test.

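### The albumin and creatinine limits in 2.1.1.13 are printed in units that exclude nobody, and albumin is not required before enrolment

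*Combined protocol and SAP*

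**What the plan says.** Section 2.1.1.13 opens with "Patients must have normal organ and marrow function as defined below" and then lists limits. Two of them matter here: serum albumin of at least 2.0 mg/dL, and creatinine of at most 1.6 mg/ml. The creatinine line is followed by OR and a second renal line, an eGFR of at least 60 mL/min/1.73 m², addressed to patients whose creatinine exceeds institutional normal when treatment starts.

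Section 2.2 introduces its list with "Assessments and procedures to confirm study eligibility should be completed as follows". The blood tests are a CBC with differential, two panels and PT/PTT. The panels are itemised: "Acute Care Panel: Sodium, potassium, chloride, bicarbonate, creatinine, glucose, BUN, eGFR" and "Hepatic Panel: Alkaline phosphatase, ALT, AST, total and direct bilirubin". Neither contains albumin.

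Albumin first appears in Section 3.4.1, under "Within 10 Days Prior to Commencing DAC-THU/Pembrolizumab Therapy", as part of "Mineral Panel Albumin, Calcium total, Magnesium total (Mg), Phosphorus". In the Appendix 3 calendar, the row that carries albumin has no mark under Screening and an X under Baseline. The rows for CBC with panels and for PT/PTT are marked in both columns.

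**The concern.** An eligibility limit should be a number that some patients could fail, and it should be tested before enrolment. The albumin criterion fails on both counts and the creatinine criterion on the first.

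Anyone who applies the printed text, such as a monitor or a programmed data check, has no working numeric limit for albumin or creatinine. Renal eligibility bears on the drug under study: Section 1.2.6 reports that "THU elimination was primarily in the urine", and the pharmacokinetics, toxicity and MTD of DAC-THU are the Phase I primary objectives (Section 1.1.1).

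The order of testing is a separate matter. If staff apply the albumin limit in the unit that was presumably intended, a patient who fails it may be found only after enrolment. That would be an avoidable deviation and could use up an accrual slot.

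**Working it through.** The plan states no figure to reproduce here. The check is a unit conversion, a reading of the OR, and a comparison of sections.

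**1. Albumin.** Input: minimum 2.0 mg/dL (2.1.1.13). Since 1 g/dL = 1000 mg/dL, the limit is 2.0 / 1000 = 0.002 g/dL. The documents give no physiological range, so I assume a deliberately wide one, 0.5 to 5 g/dL, which is 500 to 5000 mg/dL. The lowest assumed value is 500 / 2.0 = 250 times the printed limit, so every value passes. With the same numeral in g/dL, 0.5 and 1 g/dL would fail.

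**2. Creatinine.** Input: maximum 1.6 mg/ml (2.1.1.13). Since 1 mg/mL = 100 mg/dL, the limit is 1.6 × 100 = 160 mg/dL. Assumed range: 0.3 to 30 mg/dL. The printed limit is 160 / 30 = 5.3 times the highest assumed value, and 160 / 20 = 8 times a value of 20 mg/dL. Every value passes. With the same numeral in mg/dL, 2 mg/dL and above would fail this limb.

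**3. How the two renal limbs combine.** The wording allows two readings:

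| Reading | Units as printed | Same numeral in mg/dL |
|---|---|---|
| Literal OR: either limb is enough | Creatinine limb always met; eGFR limb never needed | Above 1.6, the patient must meet the eGFR limb; at or below 1.6, creatinine alone is enough |
| eGFR as an added requirement when creatinine is above institutional normal | Creatinine limb always met; eGFR limb still screens those patients | Creatinine limb and eGFR limb both screen |

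So the literal OR, with the printed unit, removes renal screening by number, and the other reading keeps part of it. Correcting the unit does not settle the matter. If institutional normal lies below 1.6 mg/dL (an assumption; the documents give no value), a patient between the two with an eGFR under 60 is eligible on the first reading and not on the second.

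**4. When albumin is tested.**

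| Place | Albumin |
|---|---|
| 2.1.1.13 | Required for eligibility |
| 2.2, tests that confirm eligibility | Not listed |
| Appendix 3, Screening column | No mark |
| 3.4.1, on-study baseline, within 10 days before treatment | Listed |
| Appendix 3, Baseline column | Marked |

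The two lists and the calendar agree with one another, so the omission is unlikely to be an accident of text extraction. Creatinine and eGFR are both in the Section 2.2 panel, so the missing test is albumin only.

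**The case against.** The unit errors and the missing screening test can be read directly from the text. The opposing case concerns their consequences, and much of it stands.

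- **A reader might infer that patients with any renal function would be admitted.** The documents do not support this. The eGFR limb is in workable units, is measured at screening, and can be read as a separate requirement for patients with raised creatinine. Exclusions 2.1.2.7 and 2.1.2.12 also let the investigator turn away patients whose laboratory abnormalities raise risk or could confound results. These safeguards are real, but they rest on judgment and do not replace an objective limit.
- **A reader might infer that none of up to 85 patients would have albumin measured before enrolment.** The text shows only that Section 2.2 does not require it. Section 3.4.1 accepts screening results in place of baseline tests, so early testing is allowed. Screening is also run under separate protocols that are not available here.
- **A reader might infer a safety gap at first dose.** Section 3.4.1 requires the mineral panel before treatment, so the gap lies between enrolment and first dose.
- **A reader might infer that the MTD would be distorted.** Urinary elimination of THU makes the question relevant, but no document quantifies how renal impairment changes exposure or how many such patients would present.
- **The two albumin harms do not add up.** If the printed unit is applied, no patient can fail after enrolment. A late failure arises only if staff apply the intended unit, and then the misprint has no practical effect on albumin.

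It can also be said that correcting the creatinine unit brings the eGFR limb back into use. That is true for patients above the creatinine limit, but the two readings would still differ for patients between institutional normal and that limit.

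**Conclusion.** The point holds as two drafting errors in operative eligibility text.

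First, as printed, the albumin limit (0.002 g/dL) and the creatinine limit (160 mg/dL) can exclude no patient. This rests on the assumed ranges above, with margins of 250-fold and at least 5.3-fold, so it does not depend on their exact ends. Whether the eGFR limb is bypassed as well depends on how the OR is read, and the text does not settle that.

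Second, albumin is an eligibility criterion that is first required after the eligibility list, at on-study baseline. A patient can therefore be enrolled before it is checked, but under Section 3.4.1 is not to be treated without a result.

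The size is modest. Discretionary exclusions and the pre-dose panel limit the practical harm, and no effect on MTD, power, type I error or sample size is shown. The errors should still be corrected, because the text is what sites and monitors must apply and the correction is nearly free.

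**What to change.** 1. The sponsor confirms the intended albumin and creatinine limits and corrects their units in 2.1.1.13. The numerals suggest g/dL and mg/dL, but that is an inference for the sponsor to confirm.
2. Add albumin to the Section 2.2 blood tests and mark it under Screening in Appendix 3.
3. Reword the link between the creatinine and eGFR lines so that it is clear whether eGFR is an alternative or an added requirement, and for which patients.

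The cost is two unit corrections, one reworded line, one added analyte and one calendar mark. Albumin can be run on blood already drawn at screening, and no design parameter changes.

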2.3 PARTICIPANT REGISTRATION AND STATUS UPDATE PROCEDURES

Registration and status updates (e.g. when a participant is taken off protocol therapy and when a participant is taken off-study) will take place per CCR SOP ADCR-2: CCR Participant Registration & Status Updates found here.

2.3.1 Treatment Assignment Procedures

Cohorts

Number	Name	Description
1	Dose-Escalation	Subjects enrolled to dose escalation cohorts
2	Dose Expansion: NSCLC with high PD-L1	NSCLC subjects with high PD-L1 tumor expression enrolled at the MTD after the MTD is established
3	Dose Expansion: NSCLC with low PD-L1	NSCLC subjects with low PD-L1 tumor expression enrolled at the MTD after MTD is established
4	Dose Expansion: EsC	EsC subjects enrolled at the MTD after MTD is established
5	Dose Expansion: MPM	MPM patients enrolled at the MTD after MTD is established

Arms

Number	Name	Description
1	Dose Escalation	DAC-THU + pembrolizumab at escalating doses
2	Dose Expansion	DAC-THU + pembrolizumab at the dose established in Arm 1

Arm Assignment

Subjects in Cohort 1 will be assigned to Arm 1.

Subjects in Cohort 2, Cohort 3, Cohort 4 and Cohort 5 will be assigned to Arm 2.

3 STUDY IMPLEMENTATION

3.1 STUDY DESIGN

This trial is unique in that it is intended to establish the rationale and conditions for the use of oral DAC-THU and pembrolizumab therapy for NSCLC, EsC, and MPM. The goal is to establish the basis for subsequent evaluation of this treatment regimen in combination with other agents targeting MDSC, or adoptive immunotherapy regimens in patients with thoracic malignancies.

Patients potentially eligible for trial will be evaluated, and undergo subsequent eligibility assessment in the Thoracic Surgery Clinic/NCI. Patients meeting eligibility criteria will undergo baseline (if fresh tumor biopsy was not performed at screening) and post treatment tumor biopsies either by percutaneous image-guided FNA techniques in Interventional Radiology (Clinical Center/NIH) or endoscopic/thoracoscopic techniques in the CC operating room by Thoracic Surgery staff using standard of care practice guidelines. Tumor biopsies may be omitted at the discretion of the PI if risks outweigh potential research benefits.

The Phase I component will be a standard 3+3 design starting with oral DAC-THU on two consecutive days (preferably Tuesday and Wednesday) for two weeks out of three weeks for 9

weeks with incremental dose escalation as shown in Section **3.1.3**. Patients with high PD-L1 tumor expression will be combined with patients with low PD-L1 tumor expression to minimize accrual numbers required for the Phase I component of the study. Pembrolizumab will be administered on Wednesday, Thursday or Friday at a fixed intravenous dose of 200 mg q 3 weeks. One cycle is three weeks; one course is 9 weeks. Treatment evaluation including repeat tumor biopsy will be performed after one course of therapy (Week 10 +/- one week). Those patients exhibiting disease progression or unacceptable toxicities will be removed from study. Patients exhibiting stable disease or disease regression will be offered an additional course of therapy followed by treatment evaluation (without mandatory biopsy). Treatment will continue in this manner until off-study criteria have been met.

Once the MTD for DAC-THU has been identified, the MTD dose level will be expanded by 4 patients to confirm safety. Then, including these 10 patients at the MTD, a total of 10 NSCLC patients with high intratumoral PD-L1 expression and 10 NSCLC patients with low intra-tumoral PD-L1 expression will be evaluated in the first stage of two separate Phase II cohorts each using a Simon optimal design (Phase II; Stage I). If 5 or more of 10 NSCLC patients with high PD-L1 expression respond to treatment, the cohort will be expanded to 23 patients (Phase II; Stage II) to determine ORR at the MTD. If 2 or more of 10 patients with low PD-L1 expression respond to treatment, the cohort will be expanded to 29 patients (Phase II; Stage II) to determine ORR at the MTD. Up to 10 EsC patients including any patients treated in the expansion cohort of the Phase I component of the trial will be accrued to a separate cohort at the MTD. If 2 or more of these 10 EsC patients respond to therapy, the protocol may be amended to enable further evaluation of the investigational treatment regimen in EsC patients. Similarly, up to 10 MPM patients including any patients treated in the expansion cohort of the Phase I component of the trial will be accrued to a separate cohort at the MTD. If 2 or more of these 10 MPM patients respond to therapy, the protocol may be amended to enable further evaluation of the investigational treatment regimen in these patients.

DA	DAC-THU/Pembro Treatment: Course 1 (and subsequent courses if indicated)						
Week	Sunday	Monday	Tuesday	Wednesday	Thursday	Friday	Saturday
1	Day 0	1	2	3	4	5	6
2	7	8	9	10	11	12	13
3	14	15	16	17	18	19	20
4	21	22	23	24	25	26	27
5	28	29	30	31	32	33	34
6	35	36	37	38	39	40	41
7	42	43	44	45	46	47	48
8	49	50	51	52	53	54	55
9	56	57	58	59	60	61	62
		57	50	33	00	01	02
10	63	64	65	66	67	68	69
		DAC/THU					
		Pembro					
		Treatment Evaluation					

3.1.1 Study Schema

Treatment evaluation including staging studies and biopsy will be performed on Days 64 and 65 +/- 7 days. DAC-THU will be given on two consecutive days as indicated, with Tuesday/Wednesday optimal but not absolute. Pembrolizumab may be administered on Wednesday, Thursday, or Friday for administrative convenience.

3.1.2 Definition of Dose Limiting Toxicity (DLT)

DLT is defined as:

- Any Grade 3 or greater toxicity that cannot be attributed to a cause other than study treatment during the first two cycles of Course 1 of DAC-THU and/or pembrolizumab therapy such as disease progression or intercurrent illness.
- Any toxicity that cannot be attributed to a cause other than study treatment (DAC-THU and/or Pembrolizumab) that results in study treatment discontinuation.

3.1.3 Dose Escalation

The revised dosing regimen selected for this trial is based on pharmacodynamic evidence of systemic hypomethylation without significant systemic toxicities mediated by oral DAC-THU in patients with sickle cell disease in a recent Phase 1 clinical trial (108), as well as experience with DAC-THU/Pembrolizumab in NSCLC (Section 1.2.11.2). The frequency of DAC-THU dosing will increase using a conventional 3+3 Phase I study design attempting to maximize systemic DNMT1 depletion while avoiding Grade 3 or greater systemic toxicities (primarily neutropenia/thrombocytopenia). *Due to the uncertainty regarding cumulative toxicities, no intrapatient escalation will be allowed.*

Dose escalation will proceed as indicated in **Table 7** using three patients per dose level (irrespective of Tumor PD-L1 expression) until DLT within the first 6 weeks (two cycles) of DAC-THU therapy is observed. If one of three patients at any given dose level experiences DLT, up to three additional patients will be treated at this dose level. If only one of six patients exhibit DLT, subsequent patients will be enrolled into the next higher dose level. As soon as two patients at any given dose level develop DLT, no additional patients will be entered at that level. Subsequent patients will be accrued into the preceding dose level; if DLT is observed in less than two of six patients treated at this lower level, this dose will represent maximum tolerated dose (MTD).

Table 7: DAC-THU Dosing Schema for High (50% or Greater) and Low (0-49%) PD-L1
Expression Groups

Dose Level	DAC	DAC	THU	THU	Frequency^
	mg/kg/course	mg/kg/day*	mg/kg/course	mg/kg/day*	wk 1,2,4,5,7,8
-1	2.0	0.17	120	10	T;W
1	2.5	0.21	120	10	T;W
2	3.0	0.25	120	10	T;W
*on days a	administered				
^ T: Tuesd	lay; W: Wednesday				

3.2 DRUG ADMINISTRATION

3.2.1 DAC-THU

Timing between THU and decitabine: Oral THU capsules should be ingested within two hours prior to or two hours after a meal followed 60 minutes later by oral decitabine capsules. The capsules are to be ingested twice weekly on consecutive days as indicated in Table 7 ('Smart Caps' that can remind patients about timing of administration should be considered for use).

